9.8.3. Management of Diabetic Ketoacidosis

Typical symptoms of diabetic ketoacidosis (DKA) are thirst or a very dry mouth, frequent urination, high blood glucose (blood sugar) levels, or high levels of ketones in the urine. DKA is an AE of special concern in this population and should be described to the patients. Home monitoring should be undertaken in the event patients experience blood glucose ≥ 240 mg/dL during an illness or in the presence of symptoms described above. Patients should call the study site if they measure moderate or high ketone values.

Diabetic Ketoacidosis (DKA) is defined by

- c) Increased serum β - hydroxybutyrate or urine ketones (above ULN)
AND
- d) serum bicarbonate (total CO_2) < 15 mmol/L **OR** blood pH < 7.3

Episodes of diabetic ketoacidosis will be adjudicated by an independent data monitor in Part 1 and Part 2.

9.8.4. Potential Cases of Drug Induced Liver Injury

Abnormal values in aspartate transaminase (AST) and/or alanine transaminase (ALT) concurrent with abnormal elevations in total bilirubin that meet the criteria outlined below, in the absence of other causes of liver injury, are considered potential cases of drug-induced liver injury. (These events should be considered important medical events and reported as serious adverse events.)

Participants who present with the following laboratory abnormalities should be evaluated further to definitively determine the etiology of the abnormal laboratory values:

- a. Participants with AST or ALT baseline values within the normal range who subsequently present with AST or ALT ≥ 3 times the upper limit of normal with a total bilirubin ≥ 2 times the upper limit of normal with no evidence of 1) hemolysis, 2) cholestasis (elevated alkaline phosphatase ≥ 2 times the upper limit of normal or not available) or 3) Gilbert's Syndrome (common benign condition associated with intermittent elevations of primarily indirect, unconjugated, bilirubin to approximately 2 \times upper limit of normal (ULN)).
- b. Participants with pre-existing AST or ALT baseline values above the normal range who subsequently present with AST or ALT ≥ 2 times the baseline values and ≥ 3

times the upper limit of normal with a total bilirubin \geq 2 times the upper limit of normal with no evidence of 1) hemolysis, 2) cholestasis (elevated alkaline phosphatase \geq 2 times the upper limit of normal or not available) or 3) Gilbert's Syndrome (common benign condition associated with intermittent elevations of primarily indirect, unconjugated, bilirubin to approximately 2 x upper limit of normal (ULN)).

Increases defined above should be confirmed with repeat testing within 48 to 72 hours. In addition to repeating AST and ALT, additional laboratory tests should include albumin, amylase, creatine kinase, total bilirubin, direct and indirect bilirubin, gamma-glutamyl transferase (GGT), international normalized ratio (INR) and alkaline phosphatase. Symptoms should be assessed.

Close observation should be immediately initiated if symptoms persist and/or repeat testing confirms the abnormalities described above. Evaluation should include repeating laboratory tests (two or three time weekly; frequency may decrease to once a week or less if abnormalities stabilize or trial drug is discontinued and the patient is asymptomatic), a detailed medical history, and physical assessment. A detailed history includes relevant information, such as history of symptoms or concurrent illnesses, concomitant medication use (including review of acetaminophen use and herbal/dietary supplements), alcohol consumption, recreational drug use, and special diets. Additionally, family history, sexual history, travel history, history of contact with a jaundiced patient, surgery, blood transfusion, history of liver or allergic disease, and work exposure, should be collected. Ruling out acute hepatitis A, B, C, D, and E infection, autoimmune or alcoholic hepatitis, nonalcoholic steatohepatitis (NASH), hypoxic/ischemic hepatopathy, Epstein-Barr virus, cytomegalovirus, herpes simplex virus, toxoplasmosis, varicella, parvovirus, biliary tract disease (gall bladder/ductal imaging may be warranted). All cases confirmed on repeat testing, with no other cause for LFT abnormalities identified at the time should be considered potential drug induced liver injury irrespective of availability of all the results of the investigations performed to determine etiology of the abnormal LFTs.

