8.7.2. Clinical Laboratory Assessments

The clinical laboratory tests listed in Table 2 will be performed at the pre-specified timepoints outlined in the [SCHEDULE OF ACTIVITIES](#) and Appendix 2 for Part 1 indicated for the specific part of the study. At all visits after giving informed consent, patient will report to the site prior to their morning meal. Unscheduled clinical lab tests may be obtained at any time during the study to assess any perceived safety concerns.

Efforts should be made to obtain all blood samples at a similar clock time (e.g., 0800 hours) at each visit to the study site.

Results that are out of range will be interpreted as “abnormal, not clinically significant (NCS),” or “abnormal, clinically significant (CS).” An abnormal laboratory result may be repeated at the PI’s or licensed physician designee’s discretion. If the abnormal laboratory result is considered clinically significant and occurs after dosing, the abnormality will be recorded as AE in the EDC.

Refer to Section 9.1 for the criteria for determining whether an abnormal laboratory test

finding should be reported as an adverse event.

All biological samples will be assayed by a Sponsor-identified laboratory using a validated analytical method. Details regarding the sample processing, handling, storage, and shipment will be described in the study-specific central laboratory manual prior to the initiation of the study.

Table 2 Laboratory Tests

Hematology	Chemistry	Glycemic markers	Urinalysis	Others
Hemoglobin	BUN	HbA1c	Specific Gravity	Pregnancy test (urine)
Hematocrit	Creatinine	Fructosamine (Part 1 and 2 only)	pH	Urine drug screen ^c
RBC Count	Ca ⁺⁺ (total)	1,5 anhydroglucitol (Part 1 and 2 only)	Glucose (qual)	
MCH, MCV, MCHC & RDW	Electrolytes (Na:K, Cl)	Fasting Ultra sensitive C-peptide (Part 1 and 2 only)	Protein (qual)	
Platelet Count	Total CO ₂ (Bicarbonate)		Blood (qual)	Lipid panel (total cholesterol, HDL-C, LDL-C, triglycerides)
WBC Count	AST/ ALT		Ketones	
Leukocyte differential (percent and total neutrophils, monocytes, eosinophils, basophils, lymphocytes)	Alkaline Phosphatase	Fasting Glucagon (Part 1 and 2 only)	Leukocyte esterase	PD Markers with MMTT (Sentinels only) ^d
	Total bilirubin		Nitrites	Ultra sensitive C-peptide
	Direct (conjugated) bilirubin ^a		Microscopy ^b	Glucose, Glucagon, GLP-1
	Uric Acid			
	Albumin			
	Total Protein			
	Ketones			
	Lactate			
	Free fatty acids			
	GGT (Part 1 and 2)			
	Fasting plasma glucose			

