9. ADVERSE EVENTS REPORTING

9.1. Adverse Events

An AE is any untoward medical occurrence in a clinical study participant administered a pharmaceutical product. Study drug treatment does not necessarily have a causal relationship with the AE. An AE, therefore, can be any unfavorable change in structure, function, or chemistry (including abnormal clinical laboratory, vital signs, or ECG findings), symptoms, signs, or diseases temporally associated with the use of a medicinal (investigational) product, whether or not related to the medicinal (investigational) product, as defined by ICH.

The criteria for determining whether an abnormal objective test finding should be reported as an adverse event are as follows:

- Test result is associated with accompanying symptoms, and/or
- Test result requires additional diagnostic testing or medical/surgical intervention, and/or
- Test result leads to a change in study dosing or discontinuation from the study, significant additional concomitant drug treatment, or other therapy, and/or

Test result is considered to be an adverse event by the Investigator or Sponsor.

Merely repeating an abnormal test, in the absence of any of the above conditions, does not constitute an adverse event. Any abnormal test result that is determined to be an error does not require reporting as an adverse event.

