9.6. Documentation of Adverse Events

The condition of each study participant will be monitored throughout the study. Signs and symptoms of possible AEs may be observed by the staff, elicited by asking an open or indirect question (e.g., “How have you been feeling?”), or volunteered by the study participant. All AEs, whether observed by the PI or study site staff, elicited from the study participant, or volunteered by the study participant, will be recorded on the adverse event page(s) of the CRF. Data will include start and end dates, concomitant medications given for the AE, PI-specified or designated licensed physician-specified severity, relationship to study drug, and action taken. All AEs should be reported to the Study Sponsor.

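### Protocol 9.8.4 counts a missing alkaline phosphatase as cholestasis, so read literally a patient with DILI-level enzymes and bilirubin fails the criteria at first presentation; the likely cost is a rare reporting delay of about 0-72 h

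*Protocol*

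**What the plan says.** Protocol 9.8.4 defines potential DILI by two criteria: (a) for patients with normal baseline AST or ALT, and (b) for patients with raised baseline values. Both need AST or ALT at least 3 x ULN (criterion b adds at least 2 x baseline) together with total bilirubin at least 2 x ULN. Both then require that there be no evidence of hemolysis, cholestasis or Gilbert's syndrome. In each, cholestasis is explained in parentheses as elevated ALP at least 2 "times the upper limit of normal or not available".

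Three provisions of the section build on these criteria:

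- **Serious reporting.** Abnormalities that meet the criteria "in the absence of other causes of liver injury" are potential DILI, and "These events should be considered important medical events and reported as serious adverse events". Protocol 9.7.1 gives 24 hours to report a serious event to the sponsor.
- **Repeat test.** "Increases defined above should be confirmed with repeat testing within 48 to 72 hours". The repeat panel includes ALP.
- **Closing rule.** "All cases confirmed on repeat testing, with no other cause for LFT abnormalities identified" at the time are to be treated as potential DILI even if some etiology results are still outstanding.

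**The concern.** The words about unavailability sit inside the description of an excluding condition. An absent laboratory value therefore works in the same direction as a high one and takes the patient out of the criteria. For a rule meant to catch concurrent aminotransferase and bilirubin rises, that is the unsafe direction. It also runs against the closing rule of the same section, under which outstanding results should not remove a case.

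What is at stake is the mandatory trigger for expedited reporting at the site. TTP399 is a liver-selective agent, SAP 7.7.4 gives treatment-emergent liver-test abnormalities special-interest status, and Part 2 may run at up to 20 sites. A trigger of this kind should not depend on each site reading past the grammar.

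**Working it through.** No figure in the plan needs reproducing. The check is a logical reading of the criteria, followed by a reporting clock.

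**Step 1. Classification as worded.** Take a patient whose AST or ALT and bilirubin are above threshold, without hemolysis or Gilbert's syndrome.

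| ALP result | Counted as cholestasis? | Criterion (a) or (b) |
|---|---|---|
| below 2 x ULN | no | met |
| 2 x ULN or more | yes | not met |
| not available | yes, by the parenthesis | not met |

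The third row is the defect. It is the same in (a) and (b), and nothing elsewhere in the protocol says that a missing ALP counts as non-cholestatic.

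**Step 2. What follows for that patient.** Serious reporting attaches to meeting the criteria, so it is not triggered at first presentation. The repeat attaches to increases. AST, ALT and bilirubin increase; the absence of hemolysis, of Gilbert's syndrome or of an ALP result is not an increase and cannot be confirmed by retesting. On that reading the repeat is still due and will normally supply the ALP. If ALP is again missing but the rises are confirmed and no other cause is found, the closing rule classes the patient as potential DILI.

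**Step 3. Reporting clock.** Inputs: 24 h for a serious report (Protocol 9.7.1) and 48-72 h for the repeat (9.8.4). Laboratory turnaround is ignored.

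- ALP in hand, other causes judged absent at the first result: report by 24 h.
- ALP missing, repeat done, then reported: 48 + 24 = 72 h to 72 + 24 = 96 h.
- Difference: 72 - 24 = 48 h to 96 - 24 = 72 h.
- If the judgment on other causes waits for the repeat in both patients, both report at 72-96 h and the difference is 0 h.

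The range on the natural reading is therefore 0-72 h.

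**Step 4. Inaction-only extreme.** Suppose the repeat is also read as requiring the full criteria, and the investigator neither retests nor acts. The next ALP would then come with the next scheduled chemistry panel (Appendix 2; nominal days, windows ignored).

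- Part 2, days 14, 42 and 84: 42 - 14 = 28 days; 84 - 42 = 42 days; about 7-10 days from Week 12 to follow-up.
- Part 1, days 14, 28, 42, 56 and 84: 14 days after each of Weeks 2, 4 and 6; 84 - 56 = 28 days after Week 8; about 7-10 days after Week 12.

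**Step 5. Frequency.** Appendix 2 puts ALP on one chemistry panel with AST, ALT and total bilirubin, so an isolated missing ALP should be uncommon at scheduled visits. The documents give no rate and none is assumed.

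**The case against.** The strongest reply is that the section corrects itself. A missing ALP is not evidence of anything, so a sensible site could find no evidence of cholestasis and report at once. The repeat is tied to the rises, and the closing rule recovers confirmed cases. The part about the repeat and the recovery stands, and it is why the likely cost is a short delay and not a lost case. The part about evidence is a fair reading of intent, but it gives the words in the parenthesis no work to do. A mandatory trigger should not rest on that.

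A second reply is that general safeguards carry no ALP condition. Appendix 3 lists AST and ALT above 3 x ULN as potentially of clinical concern. Under Protocol 8.7.2, "If the abnormal laboratory result is considered clinically significant and occurs after dosing, the abnormality will be recorded as AE in the EDC". Protocol 9.1 makes a finding an adverse event when "Test result requires additional diagnostic testing or medical/surgical intervention", and under 9.6 "All AEs should be reported to the Study Sponsor". The investigator may also judge the event serious under 9.5. Safety data are reviewed during the trial (Protocol 10.7), with roughly monthly blinded sponsor review and an independent endocrinologist for events of special concern (10.9). SAP 6.2 and 7.7.4 add medical review of listings and extra liver-test monitoring. All of this stands and makes a long gap implausible. None of it sets a 24 h reporting limit or a 48-72 h repeat for this patient.

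A reader might infer more: that the patient also loses the repeat test and could go unexamined for up to 42 days. The documents do not support that as the expected course. It needs the strict reading of the repeat trigger together with an investigator who ignores a concurrent enzyme and bilirubin rise, despite the reviews above. What survives is that the repeat trigger could be worded more explicitly, since the section also directs further evaluation to patients with the abnormalities listed in (a) and (b).

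**Conclusion.** The wording is wrong as it stands and should be corrected. In both criteria an unavailable ALP keeps a patient with DILI-level AST or ALT and bilirubin outside the definition at first presentation, so serious reporting is not triggered then. The likely effect is a rare delay of about 0-72 h. This rests on two assumptions: that the repeat is done, as its wording most naturally requires, and that laboratory turnaround is negligible.

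A reader might take 48 h as the minimum delay. That would assume that every patient with an ALP result is reported within 24 h of the first result. Serious status also depends on other causes being absent, and where that judgment waits for the repeat there is no difference.

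The matter is confined to site-level identification and reporting. The SAP 7.7.4 DILI screen uses AST or ALT with bilirubin and has no ALP condition, so the patient would still appear in the planned summary and listing. No efficacy analysis is touched.

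**What to change.** In both (a) and (b), delete the three words about unavailability. Alternatively, reword the exclusion as: *no evidence of cholestasis, i.e. ALP < 2 x ULN or not available*. Add that the AST/ALT and bilirubin elevations alone trigger the 48-72 h repeat.

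A patient with no ALP is then handled like one with ALP below 2 x ULN, and remains subject to the hemolysis, Gilbert's syndrome and other-cause conditions. The amendment should not send such patients straight to serious reporting without those conditions, since incomplete data would then face a stricter rule than complete data. Patients with a measured ALP are classified as before.

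The cost is two small wording changes and one sentence at the next protocol amendment, plus an occasional case reported as serious that later proves cholestatic. The SAP needs no change.

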9.9. Pregnancy

Any pregnancy in a female study participant or the female sexual partner of a male study participant that occurs during the study or if the site becomes aware of a pregnancy within 90 days after the final dose of study drug must be reported to the Sponsor within 72 hours of this information being reported to the study site. Any pregnancy complication or elective termination for medical reasons must be recorded as an AE or SAE (if applicable). Any pregnancy should be followed at least until delivery.

10. DATA ANALYSIS / STATISTICAL METHODS

The statistical considerations summarized in the following subsection outline the plan for data analysis of this study. A Statistical Analysis Plan (SAP) will be finalized prior to unblinding the data from the study. The SAP will supersede the protocol for analyses. Any deviations from the planned analyses will be described and justified in the final integrated

study report. The analysis plans for this study will reflect sound methodologies appropriate for an adaptive study.

Continuous variables will be presented showing number of observations available, mean, median, minimum, maximum, 1st and 3rd quartiles, and standard deviations (or standard errors, depending on the variable) by visit. Categorical variables will be presented showing frequencies and percentages by visit.

All tests will be 2-sided and use an overall study-wise $\alpha = 0.05$ unless otherwise stated. SAS Version 9.1 or later will be used. Medical dictionary for Regulatory Activities (MedDRA) Version 16.0 or later will be used for coding adverse events. Medications will be coded using WHO Drug Dictionary (WHODD) Version March 2009 or later.

This study is planned using FDA guidance *Adaptive Design for Clinical Trials for Drugs and Biologics* (draft guidance, February 2010).

10.1. Randomization

Randomization for this study is balanced. Randomization identification for the patients reflects the stage of the study for the subject (sentinel phase, Part 1, or Part 2).

Part 2 introduces a stratification into the randomization to control balance between patients who enter the study on CGM and those who do not:

There are two strata:

Patients currently on CGM with at least 2 months of experience with personal CGM without significant interruptions (i.e. > 2 consecutive weeks) prior to screening who agree to continue using their personal CGM throughout the study in addition to the Sponsor supplied CGM.

OR patients currently not using a personal CGM prior to screening who agree not to use a personal CGM during the study

10.2. Sample Size Determination

Assuming a standard deviation (SD) of 1%, 34 patients per group will provide 80% power to detect a difference between a group treated with TTP399 and the group treated with placebo of 0.7% in HbA1c using alpha = 0.049.

Randomization of 68 patients (34 patients randomized to each arm) will provide adequate power for this study to meet its objectives related to HbA1c changes.

Assuming 30% or fewer placebo-treated patients show improvement in HbA1c of 0.3% or better and assuming 60% or more patients treated with TTP399 will achieve improvement in HbA1c of 0.3% or better by Week 12, 49 patients per group will provide 80% power to

detect a difference between TTP399 and placebo. Randomization of N=120 patients into the study to be included in the Part 2 analyses provides adequate power to achieve study objectives related to responder analysis.

It is noted that the randomization stratification for part 2 will be reflected in the randomization identification with a stratum digit.

It is noted that in this adaptive study, modification is permitted.

10.3. Statistical Hypotheses

The hypotheses to be tested are as follows:

- H_{01} : The mean change from baseline to Week 12 in HbA1c for the group treated with TTP399 at the selected dose is equal to that of the placebo group.
- H_{11} : The mean change from baseline to Week 12 in HbA1c for the group treated with TTP399 at the selected dose is not equal to that of the placebo group.

10.4. Analysis Population

The sentinel phase and the part 1 (learning phase of the adaptive study) will not have formal statistical hypotheses. The hypotheses relate to part 2, and it is acknowledged that, in this adaptive study, the hypotheses may be modified after evaluation of accrued data at the start of dosing of patients randomized into Part 2.

The statistical analysis plan will provide details for populations of analysis combining patients over parts of the study. In general, each segment of the protocol has its own population of analysis.

In accordance with guidance from the International Conference of Harmonization of Technical Requirements for Registration of Pharmaceuticals for Human Use (ICH) guideline ICH E9 Statistical Principles for Clinical Trials (1998), the following population of analysis will be used for all statistical analysis:

- The full analysis set (FAS) includes all randomized patients who receive any study medication and have a baseline assessment.
- The per-protocol set (PPS) includes all patients in the FAS excluding patients who have major protocol violations.
- The safety set (SAF) includes all patients who receive any study medication.

The FAS will be used for all hypothesis tests of efficacy. The PPS is used for supportive

efficacy analysis. The SAF will be used for safety analyses. Solely to understand the influence of dropouts on study conclusions, the FAS will be partitioned into completers and dropouts. Efficacy analysis will be done as randomized. Safety analysis will be done as treated.

The FAS for Part 1 will be analyzed separately from the FAS for Part 2. Analysis and presentation will also be done for Parts 1 and 2 integrated.

10.5. Disposition, Demographic, and Baseline Data

A tabulation of patient disposition will be presented by study part and overall, including the number screened, the number randomized in each population group, the number dosed in each population group, the number who withdrew prior to completing the study, and reasons for withdrawal.

Demographic and baseline characteristics (disease history, medical history, and prior treatments for T1DM) will be summarized for all randomized patients and for the FAS.

